Detailed Protocol:

Title: Transcranial Magnetic Stimulation (TMS) in Obsessive Compulsive Disorder (OCD): mechanisms and biomarkers.

Principal Investigator: [name] MD MPH PhD

Date: August 18th, 2020

I. BACKGROUND AND SIGNIFICANCE:

Obsessive Compulsive Disorder (OCD)

Obsessive-compulsive disorder (OCD) is a severe, chronic disorder, marked by recurrent, intrusive and distressing thoughts (obsessions) and/or repetitive behaviors (compulsions). OCD among adults in the United States has an estimated lifetime prevalence of 2.3% (Ruscio et al., 2010). Available data from systematic reviews and meta-analyses support cognitive-behavioral therapy (CBT) as efficacious in reducing OCD symptoms (Abramowitz, 1997; Olantunji et al., 2013; Rosa-Alcázar et al., 2008). CBT incorporating exposure and response prevention (ERP) is the psychological treatment of choice for OCD (NICE, 2006). However, approximately 25% of patients who initiate ERP for OCD drop out (Abramowitz et al., 2005). ERP involves gradual prolonged exposure to fear-eliciting stimuli or situations while simultaneously refraining from compulsive behavior. Cognitive therapy (CT), a form of CBT that focuses on modifying dysfunctional beliefs about the presence or significance of intrusive thoughts has also proven effective in the treatment of OCD (Wilhelm et al., 2009). A comparison of effect sizes between CT and ERP suggest no significant differences between variants of CBT for OCD (Abramowitz, 1997; Olantunji et al., 2013; Rosa-Alcázar et al., 2008). Findings from meta-analytic studies of CBT for OCD suggest response rates of 50% to 75% and effect sizes ranging from 0.8 to 1.24 from pre- to post-treatment, but these effects may not be durable (Abramowitz et al., 2005; Jónsson & Hougaard, 2009; NICE, 2006; Olatunji et al., 2013; Ponniah et al., 2013). A recent meta-analysis (Olatunji et al., 2013) found the overall controlled effect size for CBT was significantly larger at posttreatment (Hedge's g = 1.39) compared to follow-up (g = 0.51).

OCD can also be treated with pharmacotherapy, and the preferential efficacy of serotonin reuptake inhibitors (SRI's) led to the so-called serotonin hypothesis (for a review of the neurochemical hypothesis of OCD see Goodman, Grice, Lapidus and Coffey, 2014). An important paradigm is moving psychiatry and the clinical neurosciences from neurochemical models of disease, which originated from clinical observations of pharmacological effects, to a more anatomical and neurophysiological circuit-based understanding of emotion, behavior, cognition and their disorders (Haber & Rauch, 2009). This paradigm shift is important not only because it provides a new understanding of the neuroscientific basis of psychiatric disorders, but also because it leads to the development of novel treatment strategies using neuromodulation of selective

circuits with device-based interventions (George & Aston-Jones, 2010). TMS is one of these treatments, allowing for the directed, noninvasive modulation of neural circuitry with relatively few and benign side effects. The need to develop biomarkers that will help us understand essential pathophysiological processes in order to develop better clinical tools is paramount. Similarly, understanding the mechanism of action of our effective interventions must be a first priority strategy to identify target mechanisms that, when modified, revert pathological states.

Transcranial Magnetic Stimulation

Transcranial Magnetic Stimulation (TMS) is a noninvasive neuromodulation modality that uses powerful and rapidly changing magnetic fields applied over the surface of the skull to generate targeted electrical currents in the brain (Camprodon et al., 2013). TMS has a well-established safety profile and it is able to modulate brain activity without surgery, anesthesia or the generation of a seizure (Rossi et al., 2009). Since its development in the mid-1980s, it has become a widely used tool for neuroscience research and for clinical applications, both diagnostic and therapeutic. In 2008, the FDA approved the use of high frequency repetitive TMS (rTMS) over the left dorsolateral prefrontal cortex (DLPFC) for the treatment of MDD (O'Reardon et al., 2007), and in 2013 the use of deep TMS H-coils for the treatment of MDD was also approved (http://www.accessdata.fda.gov/cdrh_docs/pdf12/k122288.pdf). Additionally, in 2018 the FDA also approved the use of rTMS for the treatment of OCD. TMS has been shown to be a well-tolerated and effective technique that can benefit individuals with MDD through the noninvasive modulation of disease-relevant neural circuits. Clinical and translational research has also shown good safety and efficacy for other disorders, including OCD (Berlim et al., 2013). While different cortical targets have been explored for the treatment of OCD, inhibiting the pre-Supplemental Motor Area (pre-SMA) with low frequency (1Hz) rTMS has shown the best results so far (Mantovani et al., 2010).

Nevertheless, the literature on TMS for OCD remains noisy and the clinical outcomes, while promising, need improvement. An important source for this variability is the lack of individualized methods to identify and target the appropriate cortical nodes for stimulation. Our study will address this by using individual fMRI maps to identify the target and neuronavigation technology to precisely and consistently inhibit it with TMS. Another critical variable driving these inconsistencies in the field is the lack of mechanistic understanding of the effects of TMS in OCD. A priori hypotheses about disease mechanisms have driven the choices of targets of stimulations in the published clinical trials (based on a fairly robust understanding of the circuitry involved in the pathophysiology of OCD), but most studies limited themselves to measuring clinical outcomes. While this pragmatic approach is valuable, it leaves too many open questions and requires too many assumptions. Our study will innovate by proposing a translational systems neuroscience approach to understanding not only the safety and efficacy of TMS in patients with OCD, but also the physiological and anatomical changes driving (or resisting) response and remission.

II. Specific Aims

In this proposal we will apply functional neuroimaging-guided inhibitory rTMS to the pre-SMA in patients with OCD, integrating neuroimaging, behavioral and clinical research tools in a randomized controlled clinical trial. We will assess the safety and efficacy of this novel individualized strategy, study the mechanism of action at the circuit-level, and identify biomarkers and predictors of response.

Aim 1: To assess the efficacy of fMRI-guided 1HZ rTMS over the pre-SMA:

We hypothesize that patients randomized to 6 weeks of daily 1Hz rTMS will have a greater reduction in OCD symptom severity than patients randomized to identical placebo stimulation.

Aim 2: To identify the mechanisms of action of TMS at the circuit-level:

Hypothesis 2.1: We hypothesize that decreased connectivity between the pre-SMA, the Orbito-Frontal Cortex (OFC) and dorsal Anterior Cingulate Cortex (dACC) will correlate with clinical improvement.

Hypothesis 2.2: We hypothesize that TMS would improve fear extinction retention from pre- to post-treatment, and increase functional activation of the fear extinction network during extinction recall. The extinction network includes the ventromedial prefrontal cortex (vmPFC), dACC, and hippocampus.

Aim 3: To identify biomarkers and predictors of treatment response:

Hypothesis 3.1: We hypothesize that pathological hyperconnectivity between the pre-SMA, the Orbito-Frontal Cortex (OFC) and dorsal Anterior Cingulate Cortex (dACC) will correlate with OCD symptom severity in the pre-TMS scans.

Hypothesis 3.2: We hypothesize that (a) pathological hyperconnectivity between the pre-SMA the Orbito-Frontal Cortex (OFC) and dorsal Anterior Cingulate Cortex (dACC) and (b) early reduction of this pattern after week 1 of TMS will predict positive clinical outcomes after TMS.

III. SUBJECT SELECTION

There will be two different groups of patients with OCD in this study: one will receive active stimulation and one sham stimulation (i.e. placebo). We will recruit as many patients as are needed in order to obtain 20 completers per group (i.e. 40 patients in total). We expect an early termination rate of 30%, and we will anticipate the need to recruit and consent a total of 58 patients overall.

Inclusion Criteria:

- 1) 18-65 years of age.
- 2) Proficient in English.
- 3) A diagnosis of primary OCD (as determined by SCID).
- 4) Yale-Brown Obsessive Compulsive Scale total score ≥ 16 .
- 5) Normal (or corrected) vision.
- 6) Stable OCD medication regimen or OCD medication free for \geq 12 weeks prior to study.

7) Able to give informed consent.

Exclusion Criteria:

- 1) Current or history of neurologic or psychiatric disease (e.g., mental retardation, dementia, brain damage, or other cognitive impairment) that would interfere with ability to engage in TMS
- 2) Psychopathology not appropriate for the treatment (e.g., manic episode or psychosis)
- 3) Substance abuse or dependence that is current or within the last six months or use of an illicit drug that is not prescribed, as indicated by a urine drug screen and/or clinical inference.
- 4) Use of anticonvulsants within 2 weeks prior to study (to be ruled out by a urine drug screen.
- 5) Use of Tricyclic Antidepressants (e.g. Clomipramine).
- 6) Use of psychotropic medication is allowed (except for the limitations specified on use of OCD regimens, anticonvulsants, and tricyclic antidepressants).
- 7) Documented resistance to 4 or more valid pharmacological trials of 2 or more different medication classes (e.g. SSRIs and TCAs).
- 8) Previous exposure to TMS.
- 9) Major/chronic medical conditions.
- 10) History of head injury resulting in prolonged loss of consciousness and/or neurological sequelae.
- 11) Prior neurosurgical procedure.
- 12) Metal in the body **that is ferromagnetic**, metal injury to the eyes
- 13) History of seizures.
- 14) Implanted pacemaker, medication pump, vagal stimulator, deep brain stimulator, TENS unit, or ventriculo-peritoneal shunt
- 15) Pregnancy; breastfeeding or nursing; for women of childbearing a pregnancy test (to be ruled out by urine β -HCG) will be conducted prior to study.
- 16) Currently in Cognitive Behavioral Therapy (CBT).
- 17) Diagnosis of primary sleep disorder such as primary insomnia, narcolepsy, sleep apnea, shift work sleep disorder and others. Sleep disorders such as insomnia or hypersomnia that are secondary to depression or OCD are permitted.
- 18) Current clinically significant suicidality

Recruitment:

OCD patients will be recruited from the Obsessive-Compulsive Disorder Clinic at MGH, as well as elsewhere in the hospital or in its clinics. Persons inquiring to other hospital research and clinical staff about OCD research opportunities may also be included. Subjects may be recruited from persons who have listed themselves on the RSVP for Health Recruitment Registry or ResearchMatch.org as volunteers to participate in OCD research. We may also use paid advertising on the internet, television, and Boston MBTA in order to reach out to more potential subjects. Efforts will be made to attain a mix of study participants, in terms of gender and racial/ethnic representation, that is reflective of the respective populations under study. Specifically, with regard to gender, it is anticipated that half of the subjects will be male, and half will be female. Similarly, it is anticipated that minority representation in the study cohorts will be

reflective of the respective populations under study. In the event that early recruitment efforts yield under-representation of any of the above groups, active outreach will be initiated (through advertisement) in an effort to achieve the above goals.

IV. SUBJECT ENROLLMENT

The formal recruitment will take place at the first study visit to MGH. Necessary data will be gathered for the subject identification and remuneration, including date of birth, gender, years of education, address, telephone number, and social security number. Informed consent will be obtained by doctoral level licensed clinician study-staff or study staff that are doctoral candidates under the supervision of doctoral-level licensed clinicians prior to participation in the study using the e-consent module in REDCapTM and IRB-approved consent form. If the participant agrees to participate, the consent form will be signed electronically by the research participant and the individual obtaining consent. Each participant will be emailed a copy of the signed and dated consent form.

V. STUDY PROCEDURES

This study will have 2 phases: phase 1 will be a randomized, double-blinded, placebo-control trial, and phase 2 will be an open-label trial in which all patients who did not remit after completion of phase I (regardless of treatment group), will be invited to receive an additional 6 weeks of real TMS. Remitters will be defined as those subjects who have a week six Y-BOCS score of 12 or less.

1. Subjects Assessment

All candidates for this project will undergo a comprehensive clinical evaluation including a clinical interview to establish relevant psychiatric, medical and neurological history and a structured clinical interview (Structured Clinical Interview for DSM-IV Axis I Disorders; SCID-I) to confirm psychiatric diagnoses, the Edinburgh Handedness Inventory – Short Form (EHI) to establish handedness, the Beck Depression Inventory (BDI), HAM-D, and PHQ-9 to quantify depressive symptoms, the Beck Anxiety Inventory (BAI) to quantify general anxiety symptoms, the Speilberger State Trait Anxiety Inventory (STAI) to quantify trait vs. state aspects of anxiety, the Anxiety Sensitivity Index (ASI) to quantify anxiety sensitivity, and a covid-19 impact scale to assess the effect of the coronavirus pandemic in the past week. The Yale Brown Obsessive-Compulsive Scale (YBOCS), Obsessive-Compulsive Beliefs Questionnaire-44 (OBQ), the Compulsive Behaviors Form (CBF), and Obsessive-Compulsive Inventory (OCI-R) will be used to measure OCD symptoms and severity. The Clinical Global Impressions (CGI) rating scale will be used as an additional measurement of clinical change from baseline (see detailed description below). In addition, the Rey-Osterrieth Complex Figure Test and the Stroop and Wisconsin Card Sorting tasks will be conducted to assess relevant aspects of executive function and selective attention (see detailed description below). The initial evaluation of all subjects will be audio recorded for interrater reliability, and therapist supervision purposes. The digital recordings will contain participant ID numbers but not names or other identifying information. Digital recordings will be rated and simultaneously entered in the REDCap data management system for

analysis. The digital recordings will be kept by the research team in a password-protected file and destroyed after completion of the study. When possible, assessments will be used from previous studies in the OCD program (to which participants will consent).

After the initial thorough baseline assessment, patients will be assessed longitudinally through the course of the study at weeks 2, 4, 6 and 3 months after the last TMS session. These assessments will be shorter and will include the following measures: YBOCS, OBQ, OCI-R, BDI, HAM-D, PHQ-9, and covid-19 impact scale. The Rey-Osterrieth Complex Figure Test and the Wisconsin Card Sorting and Stroop tasks will also be conducted at week 6.

As of July 8th, 2020, a majority of the clinical assessment procedures will take place virtually using Healthcare Secure ZoomTM, including the SCID-I, Y-BOCS, EHI, HAM-D, CGI, and CBF. Likewise, the following self-report instruments will be administered remotely via REDCapTM: the demographics form, OCIR, ASI, OBQ, PHQ-9, CGI – Patient Version, and covid-19 impact scale. Additionally, subjects will be screened for covid-19 symptoms before attending in-person clinical study visits (baseline, week 6, and 3-month follow-up for phases 1 and 2) by completing a covid-19 symptom attestation form via REDCapTM. Administration of the ROCF, WCST, Stroop, Goal-Oriented versus Habit-Driven Behaviors Task, BDI, BAI, STAI, and urine drug screen, however, will take place **in-person** at the MGH-main campus (Simches).

Clinical Global Impressions (CGI) scale

This global rating scale, which ranges from 1 (very much improved) to 7 (very much worse) (Rush et al, 2008), is commonly used in pharmacotherapy trials. Subjects and will complete a CGI for OCD symptoms (CGI-OCD) and for overall symptoms (CGI-global) at each assessment, captured in the CGI-Patient form. The independent evaluator will complete the CGI-OCD and CGI-global at each assessment, captured in the CGI-Clinician form. Additionally, the independent evaluator will complete a CGI-Severity (CGI-S) at baseline.

Rey-Osterrieth Complex Figure Test

The Rey-Osterrieth Complex Figure Test (ROCF; Rey, 1941 and Osterrieth, 1944) evaluates visuospatial ability, executive functioning, and memory. Subjects reproduce a complicated line drawing by copy and then by memory. Participants will be asked to copy the figure with the stimulus card present (copy trial), and later to reproduce the figure from memory at two separate time points (3 min delay and 30 min delay) followed by a recognition portion. We will score *organization* (executive function) and *accuracy* (memory) using the Savage (Savage et al., 1999) and Denman (Denman, 1984) systems, respectively. The ROCF is sensitive to change (Buhlmann et al., 2006; Park et al., 2006; Kang et al., 2003; Kuelz et al., 2006).

The Wisconsin Card Sorting Task

The Wisconsin Card Sorting Test (WCST; Grant & Berg, 1981) is a measure of executive function and strategic planning, particularly with the ability of an individual to use feedback from the environment to shift individual cognitive sets and experience goal-

directed behavior. During this 10-15 minutes test, four stimulus cards incorporating color, form, and number are presented to a subject. The subject must sort the cards according to different rules or principles and be able to change their approach throughout the test administration.

The Stroop Task

The Stroop Task (Stroop, 1935) employs both controlled (color naming) and automatic (reading) processes. Participants are asked to complete the approximately five-minute task by naming the color ink of a word while ignoring the meaning of the word. In the classic Stroop Task, all words are the names of colors. The difference in time between naming the ink of a different color-word (e.g. the word 'red' is written in blue ink) versus naming the ink of a same color-word (e.g. the word 'red' is written in red ink) demonstrates the interference of automatic reading processes on controlled color naming processes. A larger Stroop interference represents difficulty with selective attention processes, processing speed, and response inhibition (e.g. Ben-David, Nguyen, van Lieshout, 2011).

Goal-Oriented versus Habit-Driven Behaviors Task

This 20-minute computer-administered task measures whether behaviors are planned and purposeful (e.g., goal-oriented) or automatic (e.g., habit-driven). In the two-step task, participants first learn to associate certain behaviors (i.e., choosing one image of a fractal over another) with rewards. Then, the rewards are devalued, and we assess whether the participants' choices change in response to the devaluation. This task has been piloted and tested with healthy individuals (Gillan et al., 2015), as well as individuals with OCD (Gillan et al., in preparation). In order to incentivize participants during the task, a small monetary award is promised based on participation (approximately \$1, no more than \$2 per administration).

2. Patient randomization and clinical trial design

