2.1 Phase 1: Randomized placebo controlled

Patients will be randomized to receive real or sham rTMS using the variable-sized permuted blocks randomization algorithm (with a maximum block size of 4), with randomization stratified by symptom severity (Y-BOCS total score ≤31 vs. >31) and age $(\le 34 \text{ vs.} > 34 \text{ years at entry})$, to ensure balance in these factors across arms in this small study. Randomizations will be conducted in SAS using procedures outlined by Efird (2011) [Efird, J. Blocked Randomization with Randomly Selected Block Sizes. Int. J. Environ. Res. Public Health., 8, 15-20]. The randomization codes generated by our statistician/data manager for each of the 4 strata will be communicated to the study coordinator at the time of randomization (i.e. at the patient's baseline visit), based on the stratum to which the patient belongs. Patients will be blinded to their treatment arm. Patients will receive 6 weeks of daily treatments Monday through Friday (not on weekends). There will be 3 MRI sessions that will take place (i) within 2 weeks prior to the first TMS session, (ii) at the end of week 1 of treatment and (iii) within 2 weeks after the last TMS session. Longitudinal clinical assessments will take place throughout the course of study at the end weeks 2, 4 and 6 of TMS, in addition to a last assessment 3 months after TMS. Physiological assessments to measure cortical excitability and

plasticity in the motor cortex using single and paired-pulse TMS will also take place the 1st day of treatment and at the end of weeks 2, 4 and 6 of TMS.

Baseline TMS Neurophys TMS Neurophys. TMS Neurophys TMS Neurophys. 8 & 8 8 Clinical Clinical Clinical Clinical Clinical Assessment Assessment Assessment Assessment Assessment 3 mo MRI MRI MRI TMS (6 weeks) Post-TMS

Figure 1: Clinical Trial Design for Phase 1

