2.2 Phase 2: Open label TMS

Patients who do not remit following the double-blinded phase of the study will be given the option to enter an open-label phase 2 and receive an additional 6 weeks of real rTMS (regardless of whether they received real or sham TMS in phase 1). Phase 2, like phase 1, will also include an MRI session at the end of week 1 and at the end of week 6, clinical assessment at weeks 2, 4 and 6, and TMS neurophysiological assessments at the end of weeks 2, 4 and 6.

3. Transcranial Magnetic Stimulation

We will use a MagVenture MagPro X100 with MagOption stimulator and two dynamic cooled butterfly coils: one real and one sham (MagVenture, Denmark) navigated with an infrared TMS Neuronavigation Research Premium system (Localite, Germany) to administer the TMS.

We will start by measuring the patient's motor threshold (MT), which is a measure of cortical excitability used to standardize the intensity of stimulation across subjects. To do this, the TMS coil is placed over the hand representation of the primary motor cortex (M1) in a rostro-medial 45° angle. Single pulses are applied with an interpulse interval (IPI) of at least 7 seconds, to prevent additive neuromodulatory effects. When pulses are applied at suprathreshold intensities, a volley of activity travels through the pyramidal motor pathways and leads to the contraction of the contralateral hand muscle. The intensity of stimulation is sequentially reduced until we reach a point when fewer than 50% of the pulses (usually <3 out of 6) lead to a muscle contraction (identified by visual inspection or neurophysiological motor evoked potentials). The first TMS intensity that is unable to elicit a muscle contraction more than 3 out of 6 pulses is considered the motor threshold, and usually expressed as a percentage of the maximum stimulator output.

Once the MT is determined, we will define our target of stimulation using the fMRI data obtained and analyzed days prior to the first TMS session. Using the Localite TMS neuronavigation system we will corregister the patient's head to their MRI, and place the TMS coil over the scalp position that corresponds to the cortical target.

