Subjects will view two rooms presented on a monitor, both of which differ in color and content (e.g., an office and a kitchen). The conditioned stimuli (CSs) will be different cues in the room. The CS+ and the US will only be presented in one context (conditioning context; CX+). The other context will be used for extinction training (CX-). Neither CS+ presented in the context of the CX-, nor a CS- presented in either context, will ever be paired with the US. In one of the four possible CS-CX combinations, for example, the office will serve as the dangerous context, in which the subjects will receive electric currents only when the yellow light is on, whereas the kitchen will serve as the safe context, in which no electric currents will be delivered. On day 2, subjects are placed back in the magnet and will be presented with additional extinction trials to CSs in pseudorandomorder.

As of February 27th, 2018, the fear conditioning paradigm will no longer be administered to participants in this study. All fear conditioning data collected prior to February 27th will be analyzed.

VI. BIOSTATISTICAL ANALYSIS

Analysis of Aim 1: To compare change in OCD symptom severity by treatment group, we will utilize a mixed effects linear regression model with Y-BOCS total score as the outcome, a random effect for time (study week), a fixed effect for group (rTMS versus placebo stimulation), and the interaction between time and treatment group (which is the covariate of interest). We will also control for potential confounding by any covariates that are significantly imbalanced between the treatment groups.

Analysis of Aim 2.1: Specification of the analyses examining whether decreased connectivity between the pre-SMA, the Orbito-Frontal Cortex (OFC) and dorsal Anterior Cingulate Cortex (dACC) correlates with clinical improvement can be found below, in the MRI data section - Resting state Connectivity Analysis.

Analysis of Aim 2.2: Specification of the analyses examining whether TMS improves fear extinction retention from pre- to post-treatment, and whether increased functional activation of the fear extinction network (vmPFC, dACC, and hippocampus) during extinction recall can be found below, in the MRI data section - Fear Extinction.

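### Does the unstated order of the 3-month visit and open-label Phase 2 leave the Aim 1 analysis, or any planned result, undefined?

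*Combined protocol and SAP*

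**What the plan says.** Five places in the combined protocol and SAP bear on the visit, and one on the model.

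- **Section V, opening paragraph.** Phase 2 is offered to "all patients who did not remit after completion of phase I (regardless of treatment group". The threshold follows: "Remitters will be defined as those subjects who have a week six Y-BOCS score of 12 or less". The 3-month visit is not mentioned.
- **Section V.1, follow-up schedule.** Short assessments that include the Y-BOCS take place "at weeks 2, 4, 6 and 3 months after the last TMS session". No phase is named.
- **Section V.1, paragraph on remote assessment.** COVID-19 symptom screening is required before "in-person clinical study visits (baseline, week 6, and 3-month follow-up for phases 1 and 2".
- **Section V.2.1 and Figure 1.** The Phase 1 clinical assessments fall at the end of weeks 2, 4 and 6, "in addition to a last assessment 3 months after TMS". Figure 1 is the Phase 1 design and carries a 3-month post-TMS label.
- **Section V.2.2.** "Patients who do not remit following the double-blinded phase of the study will be given the option" of Phase 2, for which the text lists "clinical assessment at weeks 2, 4 and 6, and TMS neurophysiological assessments". It gives no 3-month visit and no start week.
- **Section VI, Analysis of Aim 1.** The model is a "mixed effects linear regression model with Y-BOCS total score as the outcome, a random effect for time (study week", with group and the time-by-group interaction, which is the term of interest. The visits are not listed.

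**The concern.** The 3-month Y-BOCS is the only clinical measurement after the end of stimulation, and Phase 2 gives real TMS to non-remitters of both arms. If the visit comes before Phase 2, it compares the arms as randomised. If it comes after, some sham patients have had active treatment. If Phase 2 entrants skip the Phase 1 visit, the remaining scores come from remitters and decliners, a group selected on the outcome.

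Section V.2.1 read with the opening of section V suggests one order. The week-6 remission rule allows another. Section V.1 counts the three months from a last session without saying of which phase. Because the Aim 1 model uses study week and names no visits, its wording does not strictly exclude this score. A visit that far from the others would dominate a linear slope.

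**Working it through.** **1. The plan's own figure.** Inputs from section VI, Power for the Primary Aim: 20 per group, two-sided alpha 0.05, effect size 1.06. A two-sample t-test (noncentral t, 38 df) gives power 90.4%, against the stated 90%. From section III, 40 / (1 - 0.30) = 57.1, which becomes 58 at 29 per arm, as stated. Neither figure depends on a 3-month score.

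**2. Do the sections contradict each other on order?**

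- *Opening of section V against V.2.2.* One opens Phase 2 after Phase 1 is complete, the other after the blinded phase. These can mean the same thing. The week-6 score is an eligibility criterion, not a start date.
- *V.2.1 with Figure 1.* The 3-month visit sits inside Phase 1. Phase 1 with its follow-up, then Phase 2, is therefore one coherent reading. The documents do not state it, and this review does not choose it.
- *The anchor.* Taking three months as 13 weeks, the Phase 1 visit falls at 6 + 13 = week 19. If Phase 2 ran in weeks 7-12, three months after its last session is 12 + 13 = week 25. One visit could not be at both, but the V.1 screening sentence can be read as one follow-up per phase. V.2.1 also uses the last session in a within-phase sense when it times the third Phase 1 scan.
- *V.1 against V.2.2.* This difference is real: one text has a 3-month follow-up for Phase 2 and the other does not list it. V.2.2 does not say that its list is complete.

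**3. How many patients could be affected?** The documents give no remission rate and no Phase 2 uptake, so both are assumed. With remission of 10-60%, between 40 x 0.90 = 36 and 40 x 0.40 = 16 completers are eligible. With uptake of 50-100%, between 16 x 0.50 = 8 and 36 x 1.00 = 36 enter. The range is too wide to support a statement about most patients.

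**4. What if the visit entered Aim 1 as linear week?** At weeks 0, 2, 4, 6 and 19 the mean is 31 / 5 = 6.2. The squared deviations are 38.44, 17.64, 4.84, 0.04 and 163.84, total 224.80. The last visit carries 163.84 / 224.80 = 73%. Let the arm difference grow linearly to D at week 6 and stay there. The least-squares slope is then 9.733D / 224.80 = 0.0433D per week, against D / 6 = 0.1667D, a ratio of 26%.

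Power was computed by generalised least squares for the time-by-group slope. Assumptions: random intercept and slope, 20 per arm, 38 df, week-6 change SD scaled to 1, difference 1.06 at week 6. The share of week-6 change variance due to random slopes is also assumed.

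| Slope share | Weeks 0-6 | Plus week 18 or 19, difference fully kept | Plus week 18 or 19, half kept |
|---|---|---|---|
| 0 | 93% | 85-86% | 18-19% |
| 50% | 92% | 21-24% | 7% |
| 80% | 91% | 16-17% | 6-7% |

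Entering the visit would therefore matter.

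**5. Does the plan enter it?** The Aim 1 hypothesis in section II concerns six weeks of treatment. Remission is fixed at week 6. The schedule numbers its visits in weeks up to week 6 and gives the follow-up in months, while the model's time unit is the study week. The neurophysiology paragraph in section VI lists baseline and weeks 2, 4 and 6. No aim or hypothesis in section II and no analysis in section VI names a 3-month comparison. The power paragraph does not settle the point: it names no visit for this trial, and its four-week figure belongs to the earlier trial it cites.

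**The case for a change.** The strongest opposing case is that the ambiguity costs a few sentences to remove and could be expensive if left. The model text does not exclude the 3-month score, the Y-BOCS is collected then, and the table above shows a possible fall to 16-24% power even if the full difference persists. The two Phase 2 visit lists differ in current text.

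Part of this stands. Sections V.1 and V.2.2 do differ, the start of Phase 2 is unstated, and the Aim 1 visits are not listed. The sponsor should reconcile the first two, and which order applies is for the sponsor to say.

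The rest does not carry. The power loss belongs to an analysis that the plan gives no reason to run. The selected-group problem needs full uptake of Phase 2 and no Phase 1 follow-up for entrants, which sits badly with a follow-up for each phase. The obvious remedy, tabulating 3-month scores by Phase 2 exposure, would split patients on a post-randomisation variable chosen by outcome, and so would bring in the selection it was meant to expose.

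**Conclusion.** No change to the plan follows. The surviving inconsistency is clerical: a 3-month follow-up for Phase 2 appears in one paragraph of section V.1 and is not listed in section V.2.2, and the start of Phase 2 relative to the Phase 1 follow-up is left open. The missing Aim 1 visit list is a gap that analysts would fill with baseline and weeks 2, 4 and 6. On that reading power is 91-93% under the assumed variances, in line with the stated 90%, and the targets of 40 completers and 58 recruits stand.

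The conclusion rests on two points: the primary comparison is read as the six-week one, and no planned inference is drawn from the 3-month score. The remission, uptake and variance figures above are assumptions, used only to show what would be at stake under a different reading.
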